3 BACKGROUND INFORMATION

The DEFENDO Study was aimed at evaluating the efficacy and safety of OXERVATE™ 0.002% (20 mcg/mL) cenegermin-bkbbj ophthalmic solution administered 6 times daily for 8 weeks in patients with Stage 1 neurotrophic keratitis (NK).

The current study is a long-term study evaluating the clinical outcomes of patients at 24 months and 30 months after completion of the DEFENDO Study.

NK, also known as neurotrophic keratopathy/keratitis, is a rare degenerative corneal disease caused by an impairment of corneal nerve innervation leading to a decrease or absence in corneal sensation. The cornea is an avascular tissue that is provided with the richest innervation of all body tissues via the trigeminal nerve. Corneal hypoesthesia or anesthesia and decreased reflex tearing resulting from impaired corneal innervation can lead to a corneal epitheliopathy with a subsequent breakdown of the corneal epithelium, leading to potential visual impairment. Abnormal corneal sensation and epithelial defects with a poor tendency for spontaneous healing are the primary clinical manifestations of NK, which increase the risk for corneal complications associated with vision loss such as a persistent epithelial defect (PED), ulceration, melting, perforation, and infectious keratitis. NK has been divided into three stages according to the Mackie classification scheme ([Appendix 4](#)) and treatment recommendations are based on the severity of corneal involvement. ^[1]

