8.1.3 Safety Endpoints

- AEs assessed throughout the study.
- Slit-Lamp Examination results.
- External Ocular Examination results.

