1.3.3.3 Best Corrected Distance Visual Acuity (BCDVA)

The logarithm of the minimal angle of resolution (logMAR) visual acuity score (ranged from -0.3 to 1) will be recorded at Month 24 and 30.

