2.10 Handling of Missing Data

The primary efficacy analysis will be based on observed cases (i.e. no missing data imputation).

All analyses unless specified will be conducted on an as observed case basis, that is, no further imputation of missing data will be carried out unless explicitly stated otherwise.

In the descriptive summaries, the number of subjects with missing data will be presented under the “Missing” category. Summary statistics for continuous variables will be calculated only on non-missing values. For categorical variables, missing values will be reported under the “Missing” category but not included in the denominator count when computing percentages. When continuous data will be summarized, only the non-missing values will be evaluated for computing summary statistics. Any exception will be declared.

Imputation for Missing Concomitant Medication and AE Start and Stop Days:

Missing and/or incomplete dates for concomitant medications and AEs will be imputed for calculating Start/Onset Day and Stop Day only. The Start/Onset Day and Stop Day may be used for calculating prior or concomitant medications or calculating treatment emergent AEs. Missing and/or incomplete dates will be imputed in a manner that assumes the worst case scenario (i.e. Start/Onset as close as possible to the First Study Treatment Administration and stopped such that it assumed to have lasted for the longest possible duration, taking into account that the Start/Onset date should not be after the Stop date).

Imputation for missing Stop Date:

- For a completely missing stop year (regardless of day or month) the medication/AE will be assumed to be ongoing.
- For a missing stop month (and a medication/AE that is not ‘Ongoing’) the medication/AE will be assumed to have ended the last available month of that year.
- For a missing stop day (and a medication/AE that is not ‘Ongoing’) the medication/AE will be assumed to have ended on the last day of the month if the month is available.

Imputation for missing Start/Onset Date:

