- Percentage of patients who did not achieve an improvement in corneal sensitivity at Week 8 in the DEFENDO Study who have improvement in corneal sensitivity at Month 24 and Month 30 of the long-term follow-up

The patients who did not achieve an improvement in corneal sensitivity at Week 8 and who have improvement in corneal sensitivity at Month 24 and Month 30 will be summarized as a binary goal attainment variable (Yes/No) based on the subset of patients who did not achieve an improvement in corneal sensitivity at Week 8.

- Mean change in corneal sensitivity from baseline and Week 8 at Month 24 and Month 30

The corneal sensitivity (cm) in the NEI zone of the study eye as measured by the Cochet-Bonnet aesthesiometer will be summarized as a continuous variable.

- Schirmer I change from baseline and Week 8 to Month 24 and Month 30

The Schirmer tear test result (mm) in the study eye will be summarized as a continuous variable.

- TFBUT change from baseline and Week 8 to Month 24 and Month 30

The average TFBUT result (sec) of two repeat measurements in the study eye will be summarized as a continuous variable.

- Mean change in BCDVA from baseline and Week 8 to Month 24 and Month 30

The logMAR visual acuity score in the study eye will be summarized as a continuous variable.

- Percentage of patients that achieve a 15-letter gain from baseline and Week 8 in BCDVA at Month 24 and Month 30

The patients that achieve a 15-letter gain in BCDVA will be determined based on $\text{logMAR} - \text{Baseline logMAR} \leq -0.3$. It will be analyzed using a binary goal attainment variable (Yes/No).

- IDEEL change from baseline and Week 8 at Month 24 and Month 30

Subscores will be derived for the following modules and will be calculated only if at least 50% of the items of the dimension are completed; otherwise, the scores are missing.

Module 1:

Dry eye impact on daily life (27 questions) comprising 3 QoL domains: 1.a “Daily activities limitations”, 1.b “Emotional wellbeing” and 1.c “Work limitations”. 26 questions will be considered as part of one of these 3 domains. Question 22 will not be considered part of a domain.

1.a: Daily Activities

Daily activities section	Used in calculation of domain score?
1. Doing close work in the morning or afternoon (such as crossword puzzles, reading, looking at a computer, and/or sewing)	Yes
2. Doing close work in the evening or at night	Yes
3. Driving	Yes

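### The only categorical acuity endpoint is a 15-letter gain, so no legible planned table counts the eyes that lose 15 letters

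*SAP*

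**What the plan says.** SAP section 5 plans two kinds of acuity analysis.

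- **Continuous:** "Mean change in BCDVA from baseline and Week 8 to Month 24 and Month 30", for which "The logMAR visual acuity score in the study eye will be summarized as a continuous variable". SAP 2.8 gives n, mean, median, quartiles, minimum, maximum and SD for both value and change. The output is Table 14.2.5.1.
- **Categorical:** "The patients that achieve a 15-letter gain in BCDVA will be determined based on" a logMAR change from baseline of -0.3 or lower. Tables 14.2.5.2 and 14.2.5.3 report it against baseline and Week 8, and Protocol 8.1 has the same endpoint.

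Neither document defines a category of loss. The safety endpoints in Protocol 8.1.3 are "AEs assessed throughout the study", slit-lamp results and external examination results. Acuity is not among them. Protocol section 3 says that abnormal sensation and epithelial defects "increase the risk for corneal complications associated with vision loss such as a persistent epithelial defect (PED), ulceration, melting, perforation, and infectious keratitis".

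Acuity is measured in both eyes (Protocol 7.1.1) but summarized for the study eye only. The slit-lamp and external examination tables (SAP 6.2 and 6.3) also cover the treated non-study eye.

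On the scale itself, SAP 1.3.3.3 says that a "visual acuity score (ranged from -0.3 to 1) will be recorded at Month 24 and 30". The SAP gives no rule for an eye worse than 1. For categorical variables, SAP 2.10 says that "missing values will be reported under the “Missing” category but not included in the denominator count when computing percentages".

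**The concern.** Long-term safety is a primary objective, and the protocol's background links the complications of the disease to vision loss. The responder analysis looks only in the favourable direction. An eye that has lost three lines and an eye that has not changed both fall into the No row.

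The study has one arm, so no control group shows how many gains and losses would be expected anyway. A count of gains on its own cannot separate net benefit from gains and losses that balance. A report could state stable mean acuity and a percentage with a 15-letter gain, and leave the reader unable to say how many eyes had deteriorated by the same amount.

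**Working it through.** **Inputs.** The gain threshold is -0.3 logMAR (SAP 5). There are at most 37 patients, one study eye each (Protocol synopsis; SAP 2.1). The summary statistics are those in SAP 2.8. The value of 0.02 logMAR per letter is an assumption (5 letters per 0.1 line), as the documents do not give it. All counts of losses, gains and missing eyes below are assumptions for illustration.

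**1. The plan's own figure.** 15 × 0.02 = 0.30, so -0.3 does correspond to 15 letters. The mirror threshold for loss is +0.3, because a higher logMAR is worse.

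**2. The mean.** If k of n eyes each lose 0.3, the mean change is zero when the other n - k eyes gain on average 0.3k/(n - k).

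| n | k | Offsetting mean gain | In letters | Share losing 15 letters |
|---|---|---|---|---|
| 37 | 1 | 0.3/36 = 0.008 | 0.4 | 2.7% |
| 37 | 2 | 0.6/35 = 0.017 | 0.9 | 5.4% |
| 37 | 3 | 0.9/34 = 0.026 | 1.3 | 8.1% (exact 95% CI 1.7% to 21.9%) |
| 25 | 3 | 0.9/22 = 0.041 | 2.0 | 12.0% (exact 95% CI 2.5% to 31.2%) |

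One 15-letter loss moves the mean by 0.3/37 = 0.008 logMAR.

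**3. The other statistics in Table 14.2.5.1.** Compare two cases with n = 37 and all remaining eyes unchanged.

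- Three losses and three gains of 0.3: mean 0, median 0, quartiles 0 and 0, minimum -0.3, maximum +0.3, SD = √(6 × 0.09/36) = 0.12.
- One loss and one gain of 0.3: the same mean, median, quartiles, minimum and maximum, with SD = √(2 × 0.09/36) = 0.07.

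The maximum reveals that a loss occurred in both cases. Only the SD differs, and a reader cannot recover the number of losses from it.

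**4. The gain tables.** Three gains among 37 read 3/37 = 8.1% whether the other 34 eyes include three losses or none.

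**5. Acuity worse than logMAR 1 (conditional).** If such eyes were set to 1, the largest recordable loss would be (1 - baseline)/0.02 letters: 40 from 0.2, 15 from 0.7, 10 from 0.8 and 0 from 1.0. An eye starting above 0.7 could not register a 15-letter loss. If such eyes were left missing, they would leave both the continuous summary and the percentage. With 5 gains and 3 off-chart eyes among 37, the table would read 5/34 = 14.7% instead of 5/37 = 13.5%.

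**The case against.** Loss is not invisible under this plan. Table 14.2.5.1 reports minimum and maximum, so any observed 15-letter loss appears as a maximum change of at least +0.3. Acuity is listed by patient (Listing 16.2.6.3), with both eyes shown (SAP 2.6). Missing values appear as a count, and Protocol 10.3.4 reports the percentage missing at each visit. Protocol 9.2 makes any clinically relevant worsening of a protocol parameter an adverse event. The exclusion of study endpoints in Protocol 9.4.2 concerns serious adverse events only. Corneal complications would also be sought at the slit lamp. The 15-letter gain is a protocol endpoint, and all efficacy analyses are exploratory.

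All of this stands. A reader might infer that vision is tabulated only for gains, or that serious loss is hidden. The documents do not support either.

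A reader might also infer that scores are capped at 1 and the worst eyes dropped. SAP 1.3.3.3 gives a range and not a coding rule. The Manual of Procedures, to which the protocol refers for detail, is not available here and may hold the rule. The documents give no baseline acuities, so the number of eyes affected is unknown. The denominator effect in step 5 is small.

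These safeguards still do not supply the count. The maximum shows that at least one eye lost vision, a listing leaves the tally to the reader, and the adverse event route rests on investigator judgement with no letter threshold and is tabulated by SOC and PT.

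**Conclusion.** The point holds in a limited form. Among the legible outputs (parts of the endpoint and table lists are redacted), 15-letter gains are counted and 15-letter losses are not. Neither the continuous table nor the adverse event tables would give that number.

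In the illustration, 8.1% of eyes lose 15 letters while the mean change is zero. That figure rests on three assumptions: 3 losses, all 37 patients contributing, and 0.02 logMAR per letter. It shows what the planned tables could fail to display and predicts nothing about this cohort. The exact interval shows only how imprecise such a rate would be at this size.

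The handling of acuity worse than logMAR 1 is a secondary clarification, needed only if the Manual of Procedures does not already cover it.

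**What to change.** **Main change.** Add two tables that mirror 14.2.5.2 and 14.2.5.3 for a 15-letter loss, defined as a logMAR change of +0.3 or more. Take one from baseline and one from Week 8, at Months 24 and 30, with Clopper-Pearson 95% intervals. Report the study eye and, as in the slit-lamp tables, the treated non-study eye. The tables can sit beside the gain tables, so the protocol's list of safety endpoints need not change. Specify them before database lock. If that has passed, label them as unplanned in the clinical study report, as Protocol 10.3.5 requires.

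**Secondary change, if the Manual of Procedures is silent.** State in SAP 1.3.3.3 how acuity worse than logMAR 1 is recorded, so that it is neither truncated at 1 nor set to missing. Count such an eye as a 15-letter loss only when the coded change is +0.3 or more: a fall from 0.9 to just above 1.0 is only about 5 letters. Show off-chart eyes in a separate row. Fix any assigned value in advance, because it will move the mean in so small a sample.

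**Cost.** Some SAP wording and two small tables from data already collected. The reported vision result may look slightly less favourable.

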4 questions are included in the Treatment-Related Bother scale score. If 50% (2) or fewer of the 4 questions used in the calculation of Treatment-Related Bother scale score have missing item scores, then the scale score is calculated by multiplying the mean of the non-missing item score by 25. If 3 or more of the 4 item scores are missing, then the scale score is not calculated and should be set as missing. Multiplying by 25 transforms the scale score to a 0 to 100 scale, with 0 reflecting the greatest degree of treatment related bother measurable by the scale and 100 reflecting the lowest degree of treatment-related bother.

Module 3:

Dry eye Symptom bother (20 questions) comprising a unique domain.

Symptom Bother	Used in calculation of domain score?
1.OVER THE LAST TWO WEEKS , how often did you experience dry eye symptoms?	Yes
2. Eyes that felt gritty or sandy	Yes
3. Felt like I needed to close my eyes even though I was not tired	Yes
4. Burning or stinging eyes	Yes
5. Tired eyes	Yes
6. Blurry vision	Yes
7. Itchy eyes	Yes
8. Irritated eyes	Yes
9. Eyes that felt like they had been scratched by something	Yes
10. Eye dryness	Yes
11. Mucus in, around, or coming out of my eyes	Yes
12. Puffy or swollen eyes	Yes
13. Eye redness	Yes
14. Aching or sore eyes	Yes
15. Felt like something was in my eye	Yes
16. Frequent and/or rapid blinking	Yes
17. Difficulty blinking because of little or no moisture in my eyes	Yes
18. Sensitivity to light, glare, and/or wind	Yes
19. Sensitivity to recirculated air (such as air conditioning and heat)	Yes
20. Headaches associated with dry eye symptoms	Yes

Response for question 1	Original response code	Item score
None of the time	1	0
A little of the time	2	1
Some of the time	3	2
Most of the time	4	3
All of the time	5	4

Response for questions 2 to 20	Original response code	Item score
I did not have this symptom / Not applicable	6	0
Not at all	7	1
Slightly	8	2
Moderately	9	3
Very much	10	4

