All questions are included in the Symptom Bother scale score. If 50% (10) or fewer of the 20 questions used in the calculation of Symptom Bother scale score have missing item scores, then the scale score is calculated by multiplying the mean of the non-missing item score by 25. If 11 or more of the 20 item scores are missing, then the scale score is not calculated and should be set at missing. Multiplying by 25 transforms the scale score to a 0 to 100 scale, with 0 reflecting the greatest degree of treatment related bother measurable by the scale and 100 reflecting the lowest degree of treatment-related bother.

Change from baseline and from week 8 of above defined subscores will be summarized as a continuous variable at each visit, and mean changes from baseline and from week 8 of all the subscores will be graphically presented (e.g., radar plot) for each visit.

- EQ-5D-5L change from baseline and Week 8 at Month 24 and Month 30

Change from baseline and from week 8 of each dimension score and overall score of health today will be summarized as a continuous variable at each visit, and mean changes from baseline and from week 8 of all the dimension scores will be graphically presented (e.g., radar plot) for each visit.

[REDACTED]

[REDACTED]

[REDACTED]

[REDACTED]

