14.3.2	Listing of Serious Adverse Events during Extended Follow-up	Full Analysis Set
14.3.3	Frequency Summary of Slit-Lamp Examination Results during Extended Follow-up	Full Analysis Set
14.3.4	Frequency Summary of External Ocular Examination Results during Extended Follow-up	Full Analysis Set

List of listings

Listing Number	Listing Title	Analysis Population
16.2.1.1	Subject Disposition	Full Analysis Set
16.2.1.2	Analysis Visits	Full Analysis Set
16.2.2.1	Inclusion and Exclusion Criteria Exceptions	Full Analysis Set
16.2.2.2	Protocol Deviations	Full Analysis Set
16.2.3	Analysis Populations	Full Analysis Set
16.2.4.1	Demographics	Full Analysis Set
16.2.4.2	Etiology of Neurotrophic Keratitis	Full Analysis Set
16.2.4.3	Medical and ocular history	Full Analysis Set
16.2.5	Concomitant Medications	Full Analysis Set
16.2.6.1	Fluorescein Corneal Staining and Epithelial Healing	Full Analysis Set
16.2.6.2	Corneal Sensitivity Testing	Full Analysis Set
16.2.6.3	Best Corrected Distance Visual Acuity (BCDVA)	Full Analysis Set
16.2.6.4	Tear Film Break-Up Time (TFBUT)	Full Analysis Set
16.2.6.5	Schirmer Test	Full Analysis Set
16.2.6.6	Impact of Dry Eye on Everyday Life (IDEEL)	Full Analysis Set
16.2.6.7	EQ-5D-5L	Full Analysis Set
CCI		
16.2.7	Adverse Events	Full Analysis Set
16.2.8.1	Slit-Lamp Examination	Full Analysis Set
16.2.8.2	External Ocular Examination	Full Analysis Set

List of figures

Figure Number	Figure Title	Analysis Population
14.2.1.1	Radar Plot of Mean Change from Baseline of IDEEL Subscores during Extended Follow-up	Full Analysis Set
14.2.1.2	Radar Plot of Mean Change from Week 8 of IDEEL Subscores during Extended Follow-up	Full Analysis Set
14.2.2.1	Radar Plot of Mean Change from Baseline of EQ-5D-5L Dimensions during Extended Follow-up	Full Analysis Set
14.2.2.2	Radar Plot of Mean Change from Week 8 of EQ-5D-5L Dimensions during Extended Follow-up	Full Analysis Set

Certificate Of Completion

Envelope Id: PPD

Status: Completed

Subject: Complete with DocuSign: NGF0122_SAP 2.0_Final 22Mar2024.pdf

Source Envelope:

Document Pages: 28

Signatures: 2

Envelope Originator:

Certificate Pages: 5

Initials: 0

PPD

AutoNav: Enabled

PPD

Enveloped Stamping: Disabled

PPD

Time Zone: (UTC-05:00) Eastern Time (US & Canada)

PPD

PPD

PPD

Record Tracking

Status: Original

Holder: PPD

Location: DocuSign

3/22/2024 1:20:20 PM

PPD

Signer Events**Signature****Timestamp**

PPD

PPPD

Sent: 3/22/2024 1:23:47 PM

Security Level: Email, Account Authentication

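### The IDEEL Symptom Bother score is coded so that 100 is the most bother, but the SAP says 100 is the least, so changes read by the SAP's key have the wrong sign

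*SAP*

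**What the plan says.** SAP section 5, IDEEL Module 3, defines the Symptom Bother score in three parts.

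- **Item scores.** Question 1 asks how often symptoms occurred. Its table rows, giving response code and then item score, run from "None of the time 1 0" to "All of the time 5 4". Questions 2 to 20 start at "I did not have this symptom / Not applicable 6 0" and end at *Very much*, with item score 4.
- **Scale score.** "All questions are included in the Symptom Bother scale score". The available item scores are averaged and multiplied by 25. No item is reversed.
- **Interpretation.** The resulting 0 to 100 scale is described "with 0 reflecting the greatest degree of treatment related bother measurable by the scale and 100 reflecting the lowest degree of treatment-related bother".

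The section then says that "mean changes from baseline and from week 8 of all the subscores will be graphically presented (e.g., radar plot) for each visit". SAP Appendix 2 lists the corresponding figures, among them "Radar Plot of Mean Change from Baseline of IDEEL Subscores during Extended Follow-up". IDEEL change from baseline is an endpoint in protocol section 8.1, and quality of life belongs to the secondary objective in both documents.

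**The concern.** The item table and the interpretation sentence cannot both be right. Every item has its lowest value at the best state and its highest at the worst, and a positive multiplier keeps that order. So 100 must be the greatest symptom bother, whereas the sentence makes it the least.

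The probable origin is visible. The same 0-to-100 wording appears at the end of Module 2.b (Treatment-Related Bother), where it fits. In Module 3 it also names treatment-related bother, which is not what a symptom scale measures.

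In a single-arm study with purely descriptive efficacy analyses, the direction of change is most of what a reader takes from such a score. A report that follows the SAP's key would describe symptom relief as worsening and worsening as relief. On the radar plots, a group that improved on every scale would show an inward dent on the Symptom Bother axis.

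**Working it through.** **Inputs**, all from SAP section 5: the item-score tables for the IDEEL modules, the multiplier for each scale, and the stated meaning of 0 and 100.

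**Step 1. The stated direction against the Module 3 table.** Score = (sum of item scores / 20) × 25 when all items are answered.

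- Best answer on every item: (20 × 0 / 20) × 25 = 0. The SAP calls this the greatest bother.
- Worst answer on every item: (20 × 4 / 20) × 25 = 100. The SAP calls this the lowest bother.

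The stated direction is not reproduced; both ends are reversed. Missing items change the denominator but not the direction.

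**Step 2. The same sentence in Module 2.b.** There *None of the time* scores 4 and *All of the time* scores 0, on items about being bothered by treatment. The least bothered patient scores 4 × 25 = 100 and the most bothered 0 × 25 = 0. The sentence is right in that place.

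**Step 3. Size, by a constructed example.**

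- Start: *Most of the time* on question 1 (score 3) and *Moderately* on questions 2 to 20 (score 3). Score = (20 × 3 / 20) × 25 = 75.0.
- Later: *A little of the time* on question 1 (score 1) and *Slightly* on questions 2 to 20 (score 2). Score = ((1 + 19 × 2) / 20) × 25 = (39 / 20) × 25 = 48.75.
- Change = 48.75 − 75.0 = −26.25.

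By the item table this is relief. By the SAP's sentence it is a deterioration of 26.25 points. One level on one item moves the score by 25 / 20 = 1.25 points, so the misreading applies to changes of any size.

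**Step 4. Direction of all six scores as coded.**

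| Score | Best state | Worst state |
|---|---|---|
| Daily activities | 5 × 20 = 100 | 0 × 20 = 0 |
| Emotional well-being | 4 × 25 = 100 | 0 × 25 = 0 |
| Work limitations | 4 × 25 = 100 | 0 × 25 = 0 |
| Treatment satisfaction | 4 × 25 = 100 | 0 × 25 = 0 |
| Treatment-related bother | 4 × 25 = 100 | 0 × 25 = 0 |
| Symptom bother | 0 × 25 = 0 | 4 × 25 = 100 |

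Five scores run higher = better and one runs the other way. The SAP plans to plot them together and specifies no flip or direction label.

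**Step 5. Effect of reversing the items (4 minus item score).** Each score becomes 100 minus its former value. The example goes from 100 − 75.0 = 25.0 to 100 − 48.75 = 51.25, a change of +26.25, and the table and the sentence then agree.

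**The case against.** The contradiction itself is not in dispute. The case on the other side concerns its reach.

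- **The computed values are right for the coding.** The derivation is fixed by the table and the multiplier. Only someone who interprets the result by the SAP's sentence gets the sign wrong, and the out-of-place reference to treatment may alert a careful reader. This stands: the error is one of interpretation.
- **No test result changes.** Protocol section 10.3 sets two-sided tests. One-sample t-test and signed-rank p-values, the SD and the width of the confidence interval are the same when all signs flip. This also stands.
- **The documents do not show which side is wrong.** The IDEEL user manual, cited in SAP section 10, has to decide. True, but either answer requires a correction.
- **The radar plot is a separate matter.** If only the sentence is corrected, Symptom Bother still runs against the other axes, and a label would serve as well as a flip. The mock shells, a separate working document, may already carry one. This is fair, and makes the figure a secondary step.
- **The setting is modest.** This is one of six scores under a secondary objective, in an exploratory study of at most 37 patients. Corneal healing and safety are untouched, and the SAP sets no responder definition on this score. This bears on how much damage the error could do, not on whether it exists.

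**Conclusion.** The concern holds. Module 3 is scored in one direction and interpreted in the other, and nothing elsewhere in the SAP or protocol resolves it. Computing by the table and reading by the sentence reverses the meaning of every non-zero change in one of the six IDEEL scores, at every visit, for changes from both baseline and Week 8.

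The conclusion rests only on the SAP's own tables. It assumes that the scores will be programmed from those tables and interpreted by the accompanying text. That is reasonable, since SAP section 1 says the plan supersedes the statistical considerations in the protocols. The 26.25 points are an illustration, not an expected effect.

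This must be fixed. It sits in an operative scoring rule, could put a false clinical statement into the study report, and costs very little to correct.

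**What to change.** Check the direction of Symptom Bother in the cited IDEEL user manual, then make the table and the sentence agree.

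- **If the item table is right**, replace the sentence: 0 means no symptom bother, 100 means the greatest symptom bother, and a negative change is improvement. The cost is one SAP sentence.
- **If higher is meant to be better**, reverse the items (4 minus item score) and refer to symptom bother rather than treatment-related bother. This changes the derivation, which must be applied alike to the parent-study baseline and Week 8 data and to Months 24 and 30.

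In the first case, also deal with the radar plots. Either show 100 minus the score (equivalently, the change with its sign flipped) so that outward means better on every axis, or label the Symptom Bother axis clearly as running the other way. That is one line in the figure program or a footnote. State the direction in the title or footnote of Table 14.2.6 as well.

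Neither route needs new data. The correction should be made before the IDEEL tables and figures are interpreted.
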